12.1 Analysis sets

The Full Analysis Set (FAS) comprises all participants who received at least one dose of study treatment.

The Safety Set includes all participants who received at least one dose of study treatment.

The Dose Determining Set (DDS) includes all participants from the FAS enrolled the Safety run-in part who met the minimum exposure criterion and had sufficient safety evaluations, or experienced a dose limiting toxicity (DLT) during the first 8 weeks of dosing (two cycles).

A participant has met the minimum exposure criterion if the participant has received during the first 2 cycles 2 infusions of sabatolimab at the assigned dose level in Q4W dosing regimen, and has taken at least 75 % of the planned dose of azacitidine and venetoclax (i.e. for 2 cycles: 11

doses of azacitidine out of the 14 doses planned and 21 doses of venetoclax out of the 28 doses planned).

Participants who do not experience a DLT during Cycles 1 and 2 are considered to have sufficient safety evaluations if they have been observed for at least 56 days following the first dose, and are considered by both the sponsor and investigators to have enough safety data to conclude that a DLT did not occur.

The sabatolimab and venetoclax pharmacokinetic analysis sets include all participants from the Safety Set who provide at least one evaluable sabatolimab/venetoclax PK concentration.

For a concentration to be evaluable:

- Dosing information must be properly documented (data and time of administration).
- For pre-dose samples: the sample is collected before the next dose administration.

12.2 Participant demographics and other baseline characteristics

Demographic and other baseline data including disease characteristics will be listed and summarized descriptively for all participants from the FAS. These data will be summarized by dose level of sabatolimab for the safety run-in part and for participants entering the expansion part.

Categorical data will be presented as frequencies and percentages. For continuous data, mean, standard deviation, median, minimum, and maximum will be presented. For selected parameters, 25th and 75th percentiles will also be presented.

Relevant medical histories and current medical conditions at baseline will be summarized by system organ class and preferred term.

12.3 Treatments

The Safety set will be used for the analyses below. Categorical data will be summarized as frequencies and percentages. For continuous data, mean, standard deviation, median, 25th and 75th percentiles, minimum, and maximum will be presented.

The duration of exposure to study treatment as well as each study treatment component (sabatolimab (mg), venetoclax (mg) and azacitidine (mg)) as well the dose intensity by cycle (mg/day) (derived as the ratio of actual cumulative dose and planned dose intensity per cycle) and the relative dose intensity (%) by cycle (derived as the ratio of dose intensity and planned dose intensity) will be summarized by descriptive statistics.

Concomitant medications and significant non-drug therapies prior to and after the start of the study treatment will be listed and summarized according to the Anatomical Therapeutic Chemical (ATC) classification system.

The number of participants with dose adjustments (reductions, interruptions or permanent discontinuation) for each study treatment component and the reasons will be summarized. All exposure data will be listed.

12.4 Analysis of the primary endpoint(s)

The primary objective of the Safety run-in (Part 1) of the study is to determine whether sabatolimab 400 mg and 800 mg are safe (i.e. not meeting overdose criteria) when added in combination with azacitidine and venetoclax.

The primary objective of the Expansion (Part 2) is to determine the complete remission rate (CR) of sabatolimab (800 mg Q4W) in combination with azacitidine and venetoclax. This analysis will include all participants' data from cohort 2 of the Safety run-in (Part 1) and Expansion (Part 2).

12.4.1 Definition of primary endpoints and estimands

12.4.1.1 Safety run-in (Part 1)

For the Safety run-in part, the primary endpoint is the incidence of DLTs in the first 2 cycles of treatment for participants in the DDS.

12.4.1.2 Cohort 2 of Safety run-in (Part 1) and Expansion (Part 2)

The primary clinical question of interest is the following:

Is Sabatolimab 800 mg Q4W in combination with fixed doses of azacitidine (75 mg/m² Day 1-7) and venetoclax (400 mg Day 1-14) associated with improved efficacy (i.e. CR rate $\geq = 50\%$) for participants with high or very high risk MDS?

The primary endpoint (combining data from cohort 2 of the Safety run-in (Part 1) and the Expansion (Part 2) (i.e. sabatolimab 800 mg (Q4W)) is the proportion of participants achieving a complete remission (CR) as per investigator assessment (Section 2 and Table 2-1).

The primary efficacy estimand is described by the following five attributes:

- **Population:** Adult participants not eligible for intensive chemotherapy nor for HSCT with high or very high risk MDS (IPSS-R criteria (Greenberg et al 2012)) as assessed locally by the investigator.
- Variable: Best overall response among all disease response assessments as assessed by investigator per modified IWG MDS criteria (Cheson et al 2006) up to new anti-cancer therapy (including HSCT).
- **Treatment:** Study treatment is sabatolimab 800 mg Q4W + azacitidine (75 mg/m² Day 1-7) + venetoclax (400 mg Day 1-14). Participants will continue treatment until a reason of treatment discontinuation is met (e.g. progression, unacceptable toxicity, HSCT) (Section 6.1.5).
- Intercurrent events:
 - **Study treatment modification:** all CR will be taken into account regardless of any study treatment component interruption, dose adjustment or permanent discontinuation (Section 6.1.5).
 - **Concomitant medications and supportive care:** A participant may receive blood transfusion as supportive care and prophylactic treatment as clinically indicated (e.g. antiemetics, antibiotics, antifungals, Section 6.2.1). All CR will be taken into account

regardless of any concomitant medication administration including prohibited medications.

- New anti-cancer therapy/HSCT: CR achieved after initiation of a new anti-cancer therapy or HSCT will not be taken into account.
- Summary measures: The CR rate and the 95% confidence interval (CI).

12.4.2 Statistical model, hypothesis, and method of analysis

12.4.2.1 Safety run-in (Part 1)

Dose Limiting Toxicities (DLT) analysis

Assessment of sabatolimab 400 and 800 mg (4QW) not meeting overdose criteria when added to azacitidine and venetoclax will be based on the estimation of the probability of DLT in the first 2 cycles (starting from Cycle 1 Day 8) for participants in the DDS.

The assessment in Safety run-in (Part 1) will be guided by a Bayesian analysis of DLT data for sabatolimab, azacitidine and venetoclax in the first 2 cycles (starting from Cycle 1 Day 8) of treatment. The probability of DLT is modeled using a Bayesian approach detailed in Section 16.1.

After each cohort, the posterior distributions for the risk of DLT will be summarized to provide the posterior probability that the risk of excessive toxicity (DLT rate $\geq 33\%$) is less than 25%.

The escalation with overdose control (EWOC) principle

Dosing decisions are guided by the escalation with overdose control principle (Rogatko et al 2007). A combination dose will be judged to be safe if the risk of excessive toxicity at that combination dose is less than 25%.

Prior information

A meta-analytic framework approach was used to derive the prior distribution for the singleagent sabatolimab, azacitidine and venetoclax model parameters. The prior for the logistic model parameters for this study is the conditional distribution of the parameters given the historical data (see Spiegelhalter 2004, Neuenschwander 2010, Neuenschwander 2014). Priors are derived from hierarchical models, which take into account possible differences between the studies.

A full description of the application of the meta-analytic framework approach to derive the prior distributions of the single agent sabatolimab, azacitidine and venetoclax model parameters is given Section 16.

The prior distributions for the interaction parameters were based upon prior understanding of possible drug safety interactions. These priors are fully described in Appendix Section 16.

Listing of DLTs

DLTs will be listed, and their incidence summarized by primary system organ class and worst grade (CTCAE version 5.0) Listings and summaries will be based on the DDS.

The Section 16.1 provides details of the statistical method and the probability of excessive toxicity for different scenarios in the Safety run-in (Part 1).

12.4.2.2 Cohort 2 of Safety run-in (Part 1) and Expansion (Part 2)

CR primary analysis

The CR primary analysis will be performed for participants from cohort 2 of Safety run-in (Part 1) and Expansion (Part 2) treated with sabatolimab 800 mg Q4W.

A Bayesian design will be used in order to estimate the CR rate in the FAS (Full Analysis Set) and to provide inferential summaries (e.g., mean, median, standard deviation, 95% credible intervals, and interval probabilities) based on Bayesian posterior distribution of the CR rate. Assuming a non-informative prior distribution (Beta(1,1)), the distribution of the CR rate will be updated with all available data from the participants included in the FAS.

The decision criteria for trial success are the following:

- Posterior median of CR rate is \geq 50% and
- Posterior probability that CR rate is > 39% is at least 97.5%.

The cumulative posterior distribution will be used to derive the probability that the true CR rate is superior to 50%. Based on preliminary efficacy data observed with the combination azacitidine + venetoclax (Wei et al 2019), a 50% CR rate is a reasonable threshold to be considered in this specific setting.

The results will be also presented with a frequentist formulation. The CR rate and the exact 95% confidence interval (CI) (Clopper CJ and Pearson ES 1934), as well as the 1-sided p-value will be provided on the FAS. The test will be performed using an overall one-sided 2.5% level of significance. Thus, the null hypothesis (H₀:CR \leq 39%) will be rejected if the lower bound of the two-sided 95% exact CI is >39%.

The analysis will be performed using data up to the analysis data cut-off date, which will be 6 cycles after the last participant is enrolled.

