The primary analysis on CR rate (Expansion (Part 2)) will be performed after all participants have completed at least 6 cycles of treatment with sabatolimab + azacitidine + venetoclax (see Section 12.7).

4.6 **Risks and benefits**

Venetoclax in combination with azacitidine, decitabine, or low-dose cytarabine has been approved by the FDA in 16-Oct-2020 to treat newly-diagnosed AML in adults 75 years or older,

or who have comorbidities precluding intensive induction chemotherapy. Venetoclax was initially granted accelerated approval for AML in Nov-2018.

Findings from a Phase Ib (Wei et al 2019) and retrospective clinical evaluation of venetoclax in combination with azacitidine suggested promising efficacy results in higher-risk MDS participants (Ball et al 2020, Azizi et al 2020).

The potential benefit of sabatolimab combined with HMA in MDS is suggested by early efficacy results from the study [CPDR001X2105], which showed achievement of durable complete remission or bone marrow CR in high risk MDS participants receiving sabatolimab in combination with HMA. The proportion of higher-risk MDS participants achieving CR/mCR and durable CR/mCR under treatment with sabatolimab combined with HMA appears to be larger as compared to historic and published data on similar MDS participants treated with HMA alone. As of 25-Jun-2020, among 35 evaluable participants with HR-MDS who were treated with sabatolimab in combination with HMA, the overall response rate (ORR) was 62.9%: 8 complete remissions (CR), 8 marrow CR (5 with hematologic improvement [HI]), 6 stable diseases with HI. Median time to response was 2.0 months and estimated 6-months duration of response rate for CR/mCR/PR was 90% (95% CI: 73.2-100%).

The risk to participants in this trial may be minimized by compliance with the eligibility criteria and study procedures, as well as close clinical monitoring. Further, dose modifications are provided and must be applied per protocol based on clinical or laboratory findings (see Section 6.5.3).

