Women of childbearing potential must be informed that taking the study treatment may involve unknown risks to the fetus if pregnancy were to occur during the study and agree that in order to participate in the study they must adhere to the contraception requirements for the duration of the study. If there is any question that the participant will not reliably comply, they should not be entered in the study.

Male participants, including vasectomized men, in the study, must agree not to father a child and to use a condom during intercourse, to prevent delivery of the drug via seminal fluid during the study, and for the period of 3 months after the last dose of azacitidine.

Prior to starting treatment, male participants are advised to seek consultation on sperm storage and female participants of childbearing potential should seek consultation regarding oocyte cryopreservation.

A copy of the approved version of all consent forms must be provided to Novartis/sponsor after IRB/IEC approval.

8 Visit schedule and assessments

Assessment schedule (Table 8-1) lists all of the assessments when they are performed. All data obtained from these assessments must be supported in the participant's source documentation.

Each treatment cycle is 28 days. Screening evaluations should be performed within \leq 28 days of Cycle 1 Day 1 (except for the pregnancy test which has to be performed within 72 hours before the first dose).

During the course of the study visits, test and/or procedures should occur on schedule whenever possible. A visit window of +/- 3 days is allowed for study procedures (including treatment administration). If sabatolimab administration on Day 8 is delayed within a cycle due to toxicities, visit assessments for Day 8 should be shifted accordingly or occur on Day 22, in case of no administration. See Section 6.1 for details on study treatment.

A window of +/-7 days from the planned visit date is allowed for BMA procedures. During the post-treatment and survival follow-up phases, a visit window of +/-14 days is allowed.

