Response assessment will be performed by investigator according to the assessment schedule depicted in Table 8-1. Moreover, participants can be assessed for disease response (bone marrow assessment, hematology, transfusion) at any time if clinically indicated as an example if there is a clinical suspicion of progression/relapse, in particular after a participant has achieved a CR.

Bone marrow assessments will be performed at screening and pre-dose on C3D1. From C7D1, bone marrow assessments will be performed every 3 cycles until C13D1 (C7D1, C10D1, C13D1), then every 6 cycles until C25D1 (C19D1 and C25D1) and thereafter every 12 cycles (C37D1, C49D1 etc.) and as clinically indicated during the treatment period.

Hematology assessments will be performed at screening, pre-dose on D1, D8 and D22 of Cycles 1 and 2, and thereafter pre-dose on D1 and D8 of each cycle until end of treatment.

Bone marrow and peripheral blood pathology specimens (i.e. bone marrow aspirate slides, bone marrow biopsy block if applicable, peripheral blood smears) prepared locally for the disease response assessment, should be sent to the Novartis designated central laboratory for storage. This includes specimens taken during the regular work-up of the participant and used as baseline assessment for the study as mentioned in Section 8.2. A copy of the corresponding pathology reports should be collected and sent to the Novartis designated central laboratory for storage. Central morphology review of the pathology specimens may be performed, if deemed necessary. For China only: Storage of the above pathology specimens and reports in a Novartis designated laboratory will be performed, if adequate approval has been obtained from all relevant Chinese authorities.

Participants who discontinue treatment for reasons other than documented disease progression, death, lost to follow-up, or withdrawal of consent, will enter the efficacy follow-up phase.

In the efficacy follow-up phase, hematology assessments must continue to be performed every 3 months, response should be assessed at least every 12 months, and bone marrow assessment should be done at least every 12 months thereafter per Table 8-1, or as clinically indicated any time in case disease progression is suspected. Further information about blood transfusions will be continuously collected throughout the efficacy follow-up period.

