9.2 Study completion and post-study treatment

Following completion of the safety follow-up period and/or efficacy follow-up period, all participants will be followed for survival (see Section 9.1.1.3).

The information collected is kept as source documentation. All SAEs reported during this time period must be reported as described in Section 10.1.3. Documentation of attempts to contact the participant should be recorded in the source documentation.

The CR rate analysis will be conducted after the last participant enrolled has completed 6 cycles of treatment or discontinued earlier. Following the cut-off date for the analysis reported in the primary Clinical Study Report (CSR), the study will remain open and ongoing participants will continue to receive study treatment and be followed per the schedule of assessments until discontinuation criteria is met per Section 9.1.1.

The end of study is defined as the earliest occurrence of one of the following:

 \cdot Last participant has been followed for at least 3 years or have discontinued treatment, have died, have been lost to follow-up or have withdrawn consent to further participation in the study.

 \cdot The last participant on treatment has been enrolled into a separate rollover study or another option of continued treatment with sabatolimab.

At the end of the study, in alignment with local regulations, Post Trial Access (PTA) will be set-up to provide sabatolimab outside this study through an alternative setting for participants who are still receiving treatment with sabatolimab and deriving clinical benefit in the opinion of the investigator (see Section 6.1.5).

The final analysis will occur at the end of the study. All available data from all participants up to this cut-off date will be analyzed and summarized in a final CSR.

10 Safety monitoring and reporting

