For each cohort of the safety run-in part, the primary safety analysis will be conducted when the evaluable participants would have been observed for 2 cycles of treatment. If the dose of 400 mg of sabatolimab in combination with azacitidine and venetoclax with at least 3 evaluable participants is judged to be safe, then at least 9 new evaluable participants would be needed to evaluate the safety of the 800 mg of sabatolimab in combination with azacitidine and venetoclax. Otherwise, the study will be stopped. If the 800 mg of sabatolimab is not meeting overdose criteria, Expansion (Part 2) of the study will be opened. Otherwise study will be stopped.

The primary efficacy analysis (CR rate analysis) will be performed on all participant data treated at dose level of 800 mg of sabatolimab at the time last enrolled participant will have completed at least 6 cycles of treatment or discontinued earlier.

The final efficacy and safety analyses will be conducted when last enrolled participant have been followed up for at least 3 years (see Section 9.2 for details).

Any data analysis carried out independently by the investigator should be submitted to Novartis before publication or presentation.

Categorical data will be presented as frequencies and percentages. For continuous data, mean, standard deviation, median, minimum, and maximum will be presented. For selected parameters, 25th and 75th percentiles will also be presented.

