12.7 Interim analyses

No formal interim analysis is planned for this trial. During the Expansion (Part 2), a periodic safety review by the Steering Committee will occur approximately every 6 months.

In the Safety run-in (Part 1), the first safety review meeting will be conducted after participants included in the first cohort (N=6 with at least 3 evaluable participants treated with sabatolimab at the 400 mg Q4W) have completed 2 cycles of treatment. If the 400 mg Q4W dose of sabatolimab is considered to be safe in combination with venetoclax and azacitidine guided by the Bayesian analysis based on the incidence of dose limiting toxicity (DLT) data as well as all available safety, clinical pharmacology and tolerability data a second cohort with 12 participants will be opened (sabatolimab at 800 mg Q4W), otherwise the study will be stopped.

After completion of 2 cycles of treatment with at least 9 evaluable participants, the second safety review meeting will take place. The decision will be made based on DLT observation and the Bayesian model to open the Expansion (Part 2) (or not) at this dose level (sabatolimab at 800 mg Q4W) in combination with venetoclax and azacitidine. If sabatolimab 800 mg Q4W is considered to be safe then Expansion (Part 2) will be opened at the same dose level (800 mg Q4W). Otherwise the study will be stopped.

The primary analysis on CR rate will be performed after last participant have completed 6 cycles of treatment with sabatolimab + azacitidine + venetoclax or discontinued earlier. A final analysis will be performed after last enrolled participant have been followed for 3 years or discontinued study earlier. Formal testing of the primary endpoint with full level alpha will be performed at the primary analysis. If required or requested by Health Authorities, updated analyses after the primary CR rate analysis may be conducted prior to the final analysis.

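### The protocol gives two different cut-off rules for the primary CR analysis, and neither guarantees that the last enrolees' C7D1 response assessment is included

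*Protocol*

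**What the plan says.** The timing of the primary CR analysis is stated in five places in the protocol, under two kinds of rule.

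- **Calendar rule.** Section 12.4.2.2 uses data up to the "analysis data cut-off date, which will be 6 cycles after the last participant is enrolled".
- **Completion rule.**
  - Section 9.2: "The CR rate analysis will be conducted after the last participant enrolled has completed 6 cycles of treatment or discontinued earlier".
  - Opening text of Section 12: "at the time last enrolled participant will have completed at least 6 cycles of treatment or discontinued earlier".
  - Section 12.7: "The primary analysis on CR rate will be performed after last participant have completed 6 cycles of treatment", again with earlier discontinuation allowed.
  - Section 4.5 asks that all participants "have completed at least 6 cycles of treatment with sabatolimab + azacitidine + venetoclax" and does not mention discontinuation.

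The response schedule is in Sections 8 and 8.3.1. "Each treatment cycle is 28 days". "Bone marrow assessments will be performed at screening and pre-dose on C3D1". "From C7D1, bone marrow assessments will be performed every 3 cycles until C13D1". Marrow procedures have a window of 7 days either side of the planned date. Marrow and response can also be assessed when clinically indicated, and are assessed at end of treatment (Table 8-1).

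None of the five places says that the C7D1 assessment must be in the CR data. The SAP does tie six cycles to C7D1, but only for EFS and for the blast-trend displays (SAP 2.6.1.2).

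**The concern.** After C3D1 (Day 57), the next scheduled response assessment is C7D1, 112 days later. A cut-off near Day 168 sits at the very edge of that second look. The CR rate is computed in the FAS, which keeps every treated participant in the denominator. Someone whose first CR would be seen at C7D1, but whose C7D1 falls after the cut-off, is counted as a non-CR. Success needs 36 CRs out of 70, so a few such participants could cost power. Two different rules for one primary data set also leave room for choosing the date once open-label data are visible.

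**Working it through.** **1. The plan's own figures.** With X ~ Bin(70, p) and success if X ≥ 36:
- p = 39/70 (55.7%): P(X ≥ 36) = 0.8005. The plan prints 80%.
- p = 0.386: P(X ≥ 36) = 0.0197. The plan prints 2.0%.
- Under the Beta(1,1) prior, 36/70 gives a posterior median of 51.4% and P(CR > 39%) = 0.983, as printed.

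**2. Where the dates fall** (C1D1 = Day 1):
- C3D1 = 2×28 + 1 = Day 57.
- End of cycle 6 = 6×28 = Day 168.
- C7D1 = 6×28 + 1 = Day 169, with marrow window Days 162 to 176.
- Calendar cut-off when enrolment is e days before C1D1 = 1 + 168 − e.

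| e (days) | Cut-off | Position against the C7D1 window |
|---|---|---|
| 0 | Day 169 | planned C7D1 day |
| 3 | Day 166 | inside, before the planned day |
| 7 | Day 162 | first day of the window |
| 28 | Day 141 | 21 days before the window opens |

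The protocol supports more than one value of e. Section 6.3.2 enrols through IRT before C1D1 dosing. The glossary links enrolment to consent, and screening may take up to 28 days.

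**3. How C7D1 can be lost.**
- *Late marrow.* Under the calendar rule with e = 0, a marrow on Days 170 to 176 is permitted but falls after the cut-off.
- *Cycle delay.* Section 6.5.3 tolerates a delay of up to 28 days at a cycle start, and Section 8 shifts later visits when dosing resumes. The calendar rule does not move with them.
- *Early enrolment date.* As in the table.

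The completion rule absorbs delays for the participant it names. It can still be met on Day 168, one day before planned C7D1 and eight days before its window closes (176 − 168). In Sections 9.2, 12 and 12.7 it is tied to the last enrolled participant, so a slightly earlier enrolee with long delays may not be covered.

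**4. What it could cost.** Let k be the number of participants who lose C7D1 and f the share of CRs first seen there. The documents give neither, so both are assumptions. The number of CRs is then Bin(70 − k, p) + Bin(k, p(1 − f)), and the expected fall in the rate is k·p·f/70. For k = 1 and f = 0.5 this is 0.557×0.5/70 = 0.4 points. With p = 39/70:

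| k | Fall in rate (points), f = 0.25 to 0.5 | Power, f = 0.25 to 0.5 |
|---|---|---|
| 0 | 0 | 80.0% |
| 1 | 0.2 to 0.4 | 79.1% to 78.2% |
| 3 | 0.6 to 1.2 | 77.1% to 74.1% |
| 5 | 1.0 to 2.0 | 75.1% to 69.6% |

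Type I error at 27/70 falls as well, from 1.9% to 1.7% (k = 1, f = 0.5) or 1.0% (k = 5, f = 0.5).

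**The case against.** The best defence is that on the nominal schedule almost nothing is lost. Counted from first dose, the cut-off is the C7D1 day or the day before. Four of the five statements are completion-based and set a floor rather than a fixed date. The SAP twice reads six cycles as including C7D1, so the completion wording may have been meant that way. Any error is conservative. Because best overall response has no fixed time window, every single cut-off gives late enrolees less follow-up. Most of this stands and limits the point. It does not settle which rule governs, and no text makes the SAP's reading of six cycles apply to the CR cut-off.

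A reader might infer three stronger things that the documents do not support:

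- *That the cut-off always precedes C7D1.* It clearly does so only with a late marrow, a cycle delay or an enrolment date before first dose. A delay to cycle 7 alone may not move the marrow, since Section 8 keeps assessments on calendar days while a cycle is delayed.
- *That late enrolees are judged on the C3D1 marrow alone.* Clinically indicated and end-of-treatment assessments also count, and the SAP counts unscheduled assessments towards response (2.5.1.2).
- *That power drops to 57%.* That needs k = 10 and f = 0.5. The documents give no accrual rate or delay frequency to support k = 10. The roughly two-month median time to CR cited in Section 1.1 comes from the doublet. It suggests about half of CRs arise after C3D1, but at any later time, including after C7D1, so 0.5 is close to an upper bound for f.

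**Conclusion.** The point holds as an internal inconsistency with a limited consequence. The calendar rule and the completion rule can give different data sets, and neither secures the last enrolees' C7D1 assessment. If C7D1 is lost for some of them, the CR rate is biased downward by about 0.2 to 0.4 points per affected participant, for f between 0.25 and 0.5. Power falls from 80% to the high 70s for one to three affected participants at f = 0.25, and to about 70% for five at f = 0.5. These figures hold only under the assumed k and f. There is no inflation of false success.

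The reported analysis is not affected. After the recruitment halt the expansion was not opened. The SAP uses all data to database lock (2.1), reports only the CR rate with its exact interval by dose level (2.5.2.2) and drops the formal primary CR analysis (Section 3). The defect lies in the protocol's rule for the planned 70-participant analysis.

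**What to change.** Use one rule, in the same words, in Sections 4.5, 9.2, 12, 12.4.2.2 and 12.7. The cut-off should be the date by which the last enrolled 800 mg participant, and any earlier enrolee with delayed cycles, has had the C7D1 response assessment or has discontinued earlier. State that this allows for the 7 days after the planned date and any cycle delay. Count from first dose, not from enrolment, so that the two meanings of enrolment no longer matter.

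The cost is a wording change in five places and an analysis later by about one week plus any accumulated cycle delay. Sample size, success rule and schedule of assessments stay as they are, and the SAP's abbreviated analysis needs no change.
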